#### **6.1.4 Adverse Event Collection Period**

All adverse events reported from the time of study drug administration until 30 days, following discontinuation of study drug administration have elapsed will be collected, whether solicited or spontaneously reported by the subject. In addition, serious adverse events and protocol-related nonserious adverse events will be collected from the time the subject signed the study-specific informed consent.

Adverse event information will be collected as shown in [Figure 3](#).

#### **6.1.6                   Pregnancy**

Pregnancy in a study subject must be reported to AbbVie within 1 working day of the site becoming aware of the pregnancy. Subjects who become pregnant during the study must be discontinued (Section 5.4.1).

Information regarding a pregnancy occurrence in a study subject and the outcome of the pregnancy will be collected.

Pregnancy in a study subject is not considered an adverse event. However, the medical outcome of an elective or spontaneous abortion, stillbirth or congenital anomaly is considered a serious adverse event and must be reported to AbbVie within 24 hours of the site becoming aware of the event.

Subjects and their partners should avoid pregnancy throughout the course of the study, starting with the Screening Visit through 30 days after the last study drug administration. Male subjects should refrain from donating sperm for up to 30 days post last dose of study drug. Results of a positive pregnancy test or confirmation of a pregnancy will be assessed starting with the Screening Visit through the final study visit. In the event of pregnancy occurring in the partner of an enrolled subject, written informed consent for release of medical information from the partner must be obtained prior to the collection of any pregnancy-specific information and the pregnancy will be followed to outcome.

### **6.1.7           Toxicity Management**

**Serious Infections:** Subjects should be closely monitored for the development of signs and symptoms of infection during and after treatment with study drug. Study drug should be interrupted if a subject develops a serious infection or an opportunistic infection. A subject who develops a new infection during treatment with study drug should undergo prompt diagnostic testing appropriate for an immunocompromised subject. As appropriate, antimicrobial therapy should be initiated, and the subject should be closely monitored. Re-challenge with study drug may occur once the infection has been successfully treated. If study drug administration is interrupted for more than 10 days, they should notify their study site physician, and the Investigator should consult with the study designated physician about discontinuing the subject from the study. If the subject continues in the study after an interruption > 10 days during the Induction period, he/she will be considered a non-responder and will be censored for efficacy endpoints from that point forward through the end of the study. These subjects will continue to be clinically monitored and will be evaluated in the safety analyses. Subjects who develop active tuberculosis must be withdrawn from the study immediately.

**Serious Gastrointestinal Events:** Subjects presenting with the onset of signs or symptoms of a serious gastrointestinal event should be evaluated promptly for early identification of gastrointestinal perforation.

**ECG Abnormality:** Subjects should be discontinued for an ECG change considered clinically significant.

**Management of Select Laboratory Abnormalities:** For any given laboratory abnormality, the investigator should assess the subject, apply the standard of care for medical evaluation and treatment and follow any local guidelines. Laboratory abnormalities and changes in vital signs are considered to be adverse events only if they result in discontinuation from the study, necessitate therapeutic medical intervention, (meets protocol specific criteria [see Section [6.1.7](#) regarding toxicity management]) and/or if the investigator considers them to be adverse events. Specific toxicity management guidelines for abnormal laboratory values in hemoglobin, absolute neutrophil, absolute lymphocytes, total white blood cell, platelet, liver transaminases, and serum creatinine is described per the table below (confirmation by repeat testing is required).

---

Hemoglobin	

• If confirmed < 8.0 g/dL or decrease from BL > 2.0 g/dL, interrupt study drug dosing until hemoglobin value returns to normal reference range or its Baseline value.

Absolute neutrophil count (ANC)	

• If confirmed < 1000 cells/mm^3, interrupt study drug dosing until ANC value returns to normal reference range or its Baseline value.

• Discontinue study drug if confirmed < 500 cells/mm^3.

Absolute lymphocytes counts	

• If confirmed < 500 cells/mm^3, interrupt study drug dosing until absolute lymphocytes count returns to normal reference range or its Baseline value.

Total white blood cell count	

• If confirmed < 2000 cells/mm^3, interrupt study drug dosing until white blood cell count returns to normal reference range or its Baseline value.

Platelet count	

• If confirmed < 50,000 cells/mm^3 interrupt study drug dosing until platelet count returns to > 50,000 cells/mm^3 or its Baseline value.

AST or ALT	

• Discontinue study drug if confirmed ALT or AST > 3 × ULN with a Total Bilirubin > 2 × ULN or INR > 1.5.

• Discontinue study drug if confirmed ALT or AST > 8 × ULN.

• Discontinue study drug if confirmed ALT or AST > 5 × ULN for more than 2 weeks.

Serum Creatinine (sCr)	

• If confirmed > ULN and change from BL > 1.5-fold, interrupt study drug dosing until sCr value returns to normal reference range or its Baseline value.

If the subject must undergo elective surgery, the study drug should be interrupted 1 week prior to the surgery. If the subject must undergo emergency surgery, the study drug should be interrupted at the time of the surgery. The study drug can recommence at least 1 week after surgery once the physician has examined the surgical site and determined that it has healed and there is no sign of infection.

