ABT-494 is a novel JAK1 inhibitor being developed for the treatment of adult patients with inflammatory diseases. Based on in vitro selectivity assays and in vivo animal models, ABT-494 has demonstrated that inhibiting JAK1 with minimal impact on JAK2 is feasible at efficacious drug exposure levels. Thus, the enhanced selectivity of ABT-494 has the potential for an improved benefit/risk profile by mitigating JAK2 inhibitory effects on erythropoiesis and myelopoiesis. Also, the minimum of activity of ABT-494 against JAK3, which is involved in IL-15 signal transduction cascade, could potentially minimize a decrease in NK cell counts observed with tofacitinib that may have contributed to increased incidences of viral infection, particularly reactivation of herpes zoster.

The toxicology profile of ABT-494 was initially evaluated in repeat-dose 4-week studies in rats and dogs, and the dog has been identified as the most sensitive species. Adverse findings in dogs included dose-related decreases in hemoglobin and red cell mass (red blood cell counts, hemoglobin concentration, hematocrit) and microscopic findings in popliteal lymph nodes (mixed cell infiltrates with extension into pericapsular tissues) in animals administered 3 or 5 mg/kg/day ABT-494. However, there were no changes observed for these nodes on physical exam and no systemic manifestation of this finding or evidence of this at other lymph node sites or organs.

In a 4-week toxicity study in rats, mild decreases in red blood cell counts and hemoglobin and non-adverse, dose-dependent decreases in circulating lymphocytes were observed, both effects being reversible. In rats, discolored urine, either brown or black, was observed at high doses. While this was not observed at the end of the recovery period at any dose, the significance of this observation is not known as no correlating histopathologic findings were identified. At a very high dose of 100 mg/kg/day of ABT-494 in rats, the adverse findings included mortality as well as tubular degeneration/regeneration in the kidney and liver necrosis.

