16. Subject who previously received stem cell transplantation or Subject who previously received fecal microbial transplantation in the past 1 month.
17. Subject who received non-steroidal anti-inflammatory drugs (NSAIDs) (except topical NSAIDs and the use of low dose aspirin for CV protection) within 14 days prior to Screening and during the Screening Visit.
18. Infection(s) requiring treatment with intravenous (IV) anti-infectives within 30 days prior to the Baseline Visit or oral anti-infectives within 14 days prior to the Baseline Visit.
19. Subject currently receiving total parenteral nutrition (TPN) or plan to receive TPN at any time during the course of the study.
20. Subject with positive *Clostridium difficile* (*C. difficile*) toxin stool assay during the Screening Period.
21. Screening laboratory and other analyses show any of the following abnormal results:
  - Serum Aspartate Transaminase (AST) or Alanine transaminase (ALT)  $> 1.5 \times$  upper limit of the reference range (ULN);
  - Estimated glomerular filtration rate by simplified 4-variable Modification of Diet in Renal Disease (MDRD) formula  $< 40 \text{ mL/min}/1.73 \text{ m}^2$ ;
  - Total White Blood Cell (WBC) count  $< 3,000/\mu\text{L}$ ;
  - Absolute neutrophil count (ANC)  $< 1,200/\mu\text{L}$ ;
  - Platelet count  $< 100,000/\mu\text{L}$ ;
  - Absolute lymphocytes count  $< 750/\mu\text{L}$ ;
  - Hemoglobin  $< 9 \text{ gm/dL}$ .
22. Any active or recurrent viral infection that based on the investigator's clinical assessment makes the subject an unsuitable candidate for the study, including recurrent/disseminated herpes zoster or known history of human immunodeficiency virus (HIV).

---

23. Hepatitis B (HBs Ag positive [+] or detected sensitivity on the HBV DNA PCR qualitative test for HBc Ab positive subjects) or hepatitis C (HCV RNA detectable in any subject with anti-HCV Ab).
24. Subject with active or chronic recurring infections or untreated latent TB.
25. History of moderate to severe congestive heart failure (NYHA class III or IV), cerebrovascular accident and any other condition within 6 months, which in the opinion of the Investigator, would put the subject at risk by participation in the study.

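### In the hemoglobin row of Section 6.1.7, one confirmed value can both start and end a dosing interruption, so sites can read the row in two ways

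*Protocol*

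**What the plan says.** Protocol Section 6.1.7 (Management of Select Laboratory Abnormalities) tabulates when study drug is interrupted or stopped, and notes that "confirmation by repeat testing is required".

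- **Hemoglobin, trigger:** "If confirmed < 8.0 g/dL or decrease from BL > 2.0 g/dL".
- **Hemoglobin, release:** "interrupt study drug dosing until hemoglobin value returns to normal reference range or its Baseline value". The two alternatives are joined by *or*, so either one is enough.
- **Serum creatinine, trigger:** "If confirmed > ULN and change from BL > 1.5-fold". The release has the same form as for hemoglobin: normal range or Baseline.

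Earlier in Section 6.1.7, inside the paragraph on serious infections, the protocol says: "If the subject continues in the study after an interruption > 10 days during the Induction period, he/she will be considered a non-responder". The consequence runs to the end of the study. Section 5.5.4 separately sends any interruption longer than 10 days to a consultation with the study designated physician about discontinuation. Under Sections 8.1.3 and 8.1.6.1.1, a subject who discontinues before Week 16 counts as a failure for clinical remission.

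**The concern.** A stopping rule needs a resumption rule that the triggering result does not already satisfy. Here the second trigger limb measures change from Baseline, while the first release limb measures position against the normal range. A subject who starts high can fall by more than 2.0 g/dL and never leave the normal range.

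For that subject the row supports two actions. One site sees that the release is already met and does not hold drug, or resumes at once. Another notes that a value which never left the normal range cannot return to it, and holds until Baseline is regained. The first stake is a safety rule applied differently across sites, for a parameter the sponsor watches: both SAPs list anemia as an adverse event of special interest and give hemoglobin an additional listing. The second is an indirect and conditional effect on efficacy classification.

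**Working it through.** The point concerns a rule, so the plan has no figure to reproduce. The check is whether trigger and release can both be true of one value.

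**Notation.** B = Baseline hemoglobin, L = lower limit of normal, h = confirmed value, all in g/dL.

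- Trigger: h < 8.0, or B − h > 2.0.
- Release: h ≥ L (in range; the upper limit is taken as not in play for a fallen value), or h ≥ B.

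L is not in the documents. I assume 11.5 to 14.0.

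**The four pairings**

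1. h < 8.0 and h ≥ L needs L < 8.0. This does not occur in the assumed range.
2. h < 8.0 and h ≥ B needs B < 8.0. Exclusion 21 bars hemoglobin below 9 at Screening, so this does not ordinarily arise.
3. B − h > 2.0 and h ≥ B is impossible.
4. B − h > 2.0 and h ≥ L means L ≤ h < B − 2.0. Such values exist whenever **B > L + 2.0**.

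The lowest Baseline with an overlap, on a 0.1 g/dL grid:

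| Assumed L | Lowest B with overlap |
|---|---|
| 11.5 | 13.6 |
| 12.0 | 14.1 |
| 12.5 | 14.6 |
| 13.0 | 15.1 |
| 13.5 | 15.6 |
| 14.0 | 16.1 |

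Example with L = 13.0 and B = 16.0: at h = 13.9 the fall is 16.0 − 13.9 = 2.1, and at h = 13.0 it is 3.0. Every value from 13.0 to 13.9 triggers interruption and also meets the release. Repeat testing confirms the value but leaves the overlap in place.

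**The other interruption rows**

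- *Creatinine:* a value above the upper limit cannot be in range, and a change of more than 1.5-fold cannot be at Baseline. There is no overlap.
- *Neutrophils, lymphocytes, white cells:* the triggers are absolute counts (1000, 500 and 2000 cells/mm³), below the Screening floors in exclusion 21 (1,200, 750 and 3,000/µL).
- *Platelets:* a count cannot be both below and above 50,000.

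Hemoglobin is the only interruption row that combines a stand-alone change-from-Baseline trigger with a normal-range release.

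**Path to a co-primary endpoint.** Each step is needed.

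1. The hold lasts more than 10 days in Induction. Visits at Weeks 2, 4, 8, 12 and 16 are nominally 14, 14, 28, 28 and 28 days apart, so a hold kept to the next scheduled visit can exceed 10 days. An interim retest could shorten it.
2. Then one of two routes applies:
   - The subject discontinues before Week 16. The rule that counts any such discontinuation as failure names clinical remission only.
   - The subject continues, and the non-responder sentence in the serious-infections paragraph is applied to a laboratory hold. The Induction SAP does not carry that sentence. Its Section 6.0 has a corticosteroid rule and its Section 10.2 has non-responder imputation for missing data. Under that SAP, a subject held for more than 10 days who has Week 12/16 data is classified on those data.

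The Induction SAP was written to Amendment 4. The itemized list in Appendix J shows no Amendment 5 change to Section 6.1.7, so timing does not appear to explain the gap.

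**The case against.** The strongest reply is that the row has a plain reading. The text introducing the table says it covers abnormal values, so a result inside the normal range can be taken as outside it. Because the release alternatives are joined by *or*, holding until Baseline means setting one of them aside. The same paragraph asks the investigator to assess the subject and apply standard of care, and long interruptions go to the study designated physician. On this view the drafting is loose but the rule is not contradictory.

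Part of this stands. It is fair to say that one reading may be commoner, and that consultation limits divergence once a hold passes 10 days. It does not settle the row. A fall of more than 2.0 g/dL can itself be the abnormality the table means. The release also speaks of the value returning to the normal range, which fits poorly with a value that never left it. If in-range values are outside the table, the fall limb has no effect for these subjects until the value drops below normal, and the row does not say so. Neither SAP resolves it.

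The objection is also right about reach. The non-responder sentence sits among infection rules, applies only to subjects who continue, and is missing from the Induction SAP.

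**Conclusion.** The overlap is real and follows from the wording alone. It needs only a Baseline more than 2.0 g/dL above the laboratory's lower limit; the limits tabulated above are assumptions. The row should be corrected because it is a safety rule that can release itself on the value that triggers it.

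The number of subjects affected cannot be estimated, since reference limits, Baseline hemoglobin and the frequency of confirmed falls are not given. It is likely small, because a high Baseline, a confirmed fall and a value still in range must coincide.

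A reader might infer more than the documents support:

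- **That a co-primary result turns on this row.** It could for an individual subject, but only through the steps set out above. One subject is 1/35 = 2.9 percentage points of an arm. That is a unit of scale, not an expected shift.
- **That the high-dose arms are hit more often.** Section 3.0 reports "Adverse findings in dogs included dose-related decreases in hemoglobin and red cell mass" in 4-week studies. It also reports only a mild, non-adverse red-cell decrease over 9 months in dogs, and no clinically meaningful laboratory changes in healthy volunteers given up to 24 mg BID for 14 days. Imbalance by dose is conceivable but not documented.
- **That the platelet row has the same fault.** Its release is the other side of its trigger. Its Baseline alternative is ordinarily idle given the Screening floor of 100,000, but it contradicts nothing.

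**What to change.** 1. The sponsor's clinical team should reconcile the trigger and the resumption criterion in the hemoglobin row so that one confirmed value cannot meet both. Which limits apply is theirs to decide; none is proposed here.
2. Issue that single reading to all sites, so that holds are started and ended in the same way in every arm.
3. Reconcile Section 6.1.7 with the Induction SAP on whether the more-than-10-day non-responder rule applies to laboratory holds, and state the answer in both documents.

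The cost is a clarification of one table row, a site communication, and a matching sentence in the protocol and the Induction SAP. No tests or visits are added.

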### **6.1.8                   Cardiac Adjudication Committee**

An independent committee of physician experts in cardiac adjudication will be utilized to assess cardiovascular adverse events in a blinded manner as defined by the Cardiac Adjudication Committee charter.

### **6.1.9                   Independent Data Monitoring Committee**

An external Independent Data Monitoring Committee (DMC) comprised of persons independent of AbbVie and with relevant expertise in their field will review unblinded safety data from the ongoing studies. The primary responsibility of the DMC will be to protect the safety of the subjects participating in this study.

A separate DMC charter will be prepared outside of the protocol and will describe the roles and responsibilities of the DMC members, frequency of data reviews, and relevant safety data to be assessed.

Communications from the DMC to the Study Teams will not contain information that could potentially unblind the team to subject treatment assignments.

## **6.2                   Product Complaint**

### **6.2.1               Definition**

A Product Complaint is any Complaint (see Section [6.0](#) for the definition) related to the biologic or drug component of the product.

For a product this may include, but is not limited to, damaged/broken product or packaging, product appearance whose color/markings do not match the labeling, labeling discrepancies/inadequacies in the labeling/instructions (example: printing illegible), missing components/product, or packaging issues.

Any information available to help in the determination of causality to the events outlined directly above should be captured.

### **6.2.2               Reporting**

Product Complaints concerning the investigational product must be reported to the Sponsor within 24 hours of the study site's knowledge of the event via the Product Complaint form. Product Complaints occurring during the study will be followed-up to a satisfactory conclusion. All follow-up information is to be reported to the Sponsor (or an

authorized representative) and documented in source as required by the Sponsor. Product Complaints associated with adverse events will be reported in the study summary. All other complaints will be monitored on an ongoing basis.

Product Complaints may require return of the product with the alleged complaint condition. In instances where a return is requested, every effort should be made by the investigator to return the product within 30 days. If returns cannot be accommodated within 30 days, the site will need to provide justification and an estimated date of return.

[figure not shown]
The description of the complaint is important for AbbVie in order to enable AbbVie to investigate and determine if any corrective actions are required.

## **7.0      Protocol Deviations**

AbbVie does not allow intentional/prospective deviations from the protocol. The principal investigator is responsible for complying with all protocol requirements, and applicable global and local laws regarding protocol deviations. If a protocol deviation occurs (or is identified) after a subject has been enrolled, the principal investigator is responsible for notifying Independent Ethics Committee (IEC)/Independent Review Board (IRB) regulatory authorities (as applicable), and the following AbbVie Clinical Monitor(s):

Primary Contact:

Alternate Contact:

Such contact must be made as soon as possible to permit a review by AbbVie to determine the impact of the deviation on the subject and/or the study.

For the purposes of this protocol, reportable deviations are defined as:

- Subject entered into the study even though she/he did not satisfy entry criteria.
- Subject who developed withdrawal criteria during the study and was not withdrawn.
- Subject who received wrong treatment or incorrect dose.
- Subject who received excluded or prohibited concomitant treatment.

## **8.0 Statistical Methods and Determination of Sample Size**

### **8.1 Statistical and Analysis Plans**

The objectives of the statistical analyses are to evaluate the efficacy and safety of ABT-494 versus placebo and to assess the pharmacokinetics (PK) of multiple doses of ABT-494 following oral administration in subjects with moderately to severely active Crohn's disease who have failed or are intolerant to immunomodulators or anti-TNF therapy.

Complete, specific details of the statistical analysis will be described and fully documented in the Statistical Analysis Plan (SAP). The SAP will be finalized prior to the database lock.

Unless otherwise specified, statistical tests will be one-sided significance level of 0.05 for efficacy analyses and two-sided of significance level of 0.05 for all other analyses. A test will be deemed significant if the  $P$  value rounded to three decimal places is less than or equal to 0.050 unless otherwise specified. The SAS System will be used to perform the statistical analyses.

An interim analysis of the primary and secondary efficacy variables as well as safety and pharmacodynamics biomarker data collected from Baseline through Week 16 will be performed after the last subject randomized into Study M13-740 completes the 16-week double-blind, placebo-controlled induction period in this study (Section 8.1.10). A second interim analysis of the secondary efficacy variables for the double-blind extension period, may be performed after 100% of subjects who were re-randomized at Week 16 completes Week 36 of the double-blind extension period in Study M13-740.

